6.3 Dose Modifications for Selinexor

See Section 18 (Appendix 16) for supportive care and dose modification recommendations during the Maintenance Phase of the study (Version ≥3.2).

Toxicity will be graded according to NCI CTCAE, v.4.03; the therapy modifications described below are applied according to this severity grading.

If more than one different type of toxicity occurs concurrently, the most severe grade will determine the modification.

Re-escalation of the study drug is only allowed as outlined in the sections that apply for the specific toxicity. If toxicity requires a treatment delay of more than 4 weeks the patient is taken off protocol treatment.

Each dose modification or treatment delay has to be documented in the eCR, including the respective reason.

Based on observations from the ongoing Phase 1 studies in patients with advanced hematological and solid tumors, selinexor (KPT-330) shows a wide therapeutic range, with documented anti-cancer activity from ~ 12 mg/m² to ≥ 50 mg/m² orally twice weekly. At the time of Part 1 it could not be predicted which patient's tumors would respond to lower doses, nor could tolerability be predicted. Therefore, in order to individualize and optimize therapeutic benefit with selinexor, initiation of study therapy occurred at a dose just below the MTD (50 mg/m² twice weekly by mouth). To optimize specific anti-tumor activity and the patient's tolerability, dose and/or schedule modifications were allowed. Based on preliminary findings from this study and other studies, the dosing in Part 2 was modified as follows: Part 2 Schedule 1 to 35 mg/m² twice weekly, Part 2 Schedule 1 to 50 mg/m² once weekly. Dose modifications are allowed as described in Table 2 and Table 3.

Patients should also be treated aggressively with supportive care to reduce toxicities.

Patients will continue to receive selinexor until they need to have their dose reduced below the 35 mg/m² once weekly (reduced) dose in Part 1 and Part 2 (Schedules 1 and 2), at which time treatment will be discontinued.

Table 2: Pre-specified Dose/Schedule Modifications for AEs Related to Study Drug in Part 1

Dose Level	Dose of Selinexor
Dose level 0	50 mg/m ² twice weekly (D1, D3)
Dose level -1	35 mg/m ² twice weekly (D1, D3)
Dose level -2	50 mg/m ² once weekly (D1)
Dose level -3	35 mg/m ² once weekly (D1)
Dose level -4	Discontinue dosing ^a

^a Patient discontinues treatment, but continues to be assessed.

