Table 3: Pre-specified Dose/Schedule Modifications for AEs Related to Study Drug in Part 2

Dose Level	Schedule 1	Schedule 2
Dose level 0 (Starting dose)	35 mg/m ² twice weekly	50 mg/m ² once weekly
Dose level -1	50 mg/m ² once weekly	35 mg/m ² once weekly
Dose level -2	35 mg/m ² once weekly	Discontinue dosing ^a
Dose level -3	Discontinue dosing ^a	Not applicable

^a Patient discontinues treatment, but continues to be assessed.

6.3.1 Inpatient Dose Escalation:

Inpatient dose escalation can be considered after 12 weeks for patients in Part 1 and after 6 weeks for patients in Part 2 if the patient has not experienced a major toxicity; this requires approval of the Sponsor. Inpatient dose escalations will be permitted as follows:

Part 1: Dose increase to 60 mg/m² twice weekly in each week of a 4-week cycle.

Part 2 Schedule 1: Dose increase to 50 mg/m² twice weekly in each week of a 4-week cycle (8 doses total).

Part 2 Schedule 2: Dose increase to 60 mg/m² once weekly in each week of a 4-week cycle (4 doses total).

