Grade 1 (despite maximal anti-diarrheal medication)	At the first sign of abdominal cramping, loose stools, or onset of diarrhea, it is recommended that the patient be treated according to institutional standard of care. Maintain dose level of selinexor.	At the first sign of abdominal cramping, loose stools, or onset of diarrhea, it is recommended that the patient be treated according to institutional standard of care. Maintain dose level of selinexor.	At the first sign of abdominal cramping, loose stools, or onset of diarrhea, it is recommended that the patient be treated according to institutional standard of care. Maintain dose level of selinexor.

Grade 2 (despite maximal anti-diarrheal medication)	First occurrence: reduce selinexor to once weekly until resolved to ≤ grade 1, then re-start twice weekly at the current dose level. Second occurrence: reduce selinexor dose by one dose level and dose once weekly until resolved to ≤ grade 1, then re-start twice weekly at reduced dose level	First occurrence: reduce to selinexor to once weekly until resolved to ≤ grade 1, then re-start twice weekly at the current dose level. Second occurrence: reduce selinexor dose by one dose level and dose once weekly until resolved to ≤ grade 1, then re-start twice weekly at reduced dose level	First occurrence: reduce selinexor to 35 mg/m ² until resolved to ≤ grade 1 or baseline, then re-start at the Dose level 0. Second occurrence: reduce one dose level
Grade 3/4 (despite maximal anti-diarrheal medication)	Delay selinexor until resolved to ≤ grade 2 or baseline, then follow guidelines above.	Delay selinexor until resolved to ≤ grade 2 or baseline, then follow guidelines above.	Delay selinexor until resolved to ≤ grade 2 or baseline then reduce one dose level.
Other selinexor-related adverse events			
Grade 1 or 2	Maintain dose level and initiate standard supportive care.	Maintain dose level and initiate standard supportive care.	Maintain dose level and initiate standard supportive care.
Grade 3	Delay dose until resolved to ≤ grade 1 or baseline, then reduce by one dose level.	Delay dose until resolved to ≤ grade 1 or baseline, then reduce by one dose level.	Delay dose until resolved to ≤ grade 1 or baseline, then reduce to Dose level -1.

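### The restart rule for recurrent Grade 2 diarrhea in Part 2 Schedule 1 (Protocol Table 4) calls for a twice-weekly reduced level that Table 3 does not contain

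*Protocol*

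**What the plan says.** Protocol Section 6.3.2, Table 4, uses the same text for Grade 2 diarrhea (despite maximal anti-diarrheal medication) in the Part 1 and Part 2 Schedule 1 columns.

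- **First occurrence:** go to once weekly until grade 1 or less, "then re-start twice weekly at the current dose level".
- **Second occurrence:** go down one level and dose once weekly until grade 1 or less, "then re-start twice weekly at reduced dose level".
- **Grade 3/4:** hold until grade 2 or less "or baseline, then follow guidelines above".

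The Schedule 2 column differs. At a first occurrence the patient takes 35 mg/m² until recovery, "then re-start at the Dose level 0".

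The levels are defined in Section 6.3, in Table 2 ("Pre-specified Dose/Schedule Modifications for AEs Related to Study Drug in Part 1") and Table 3 ("Pre-specified Dose/Schedule Modifications for AEs Related to Study Drug in Part 2"). Each level fixes both an amount and a weekly frequency. Section 6.3 also states: "Dose modifications are allowed as described in Table 2 and Table 3". On going back up, it states: "Re-escalation of the study drug is only allowed as outlined in the sections that apply for the specific toxicity".

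**The concern.** Table 4 relies on the ladders for what a dose level is, and in Schedule 1 the two do not fit together. A site with a Schedule 1 patient at the starting dose who has a second episode cannot both restart twice weekly and be at a reduced Table 3 level. Different sites could settle on different doses for the same event.

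Table 4 labels diarrhea as common, and this rule governs re-dosing after it recurs. Section 1.3 says the Part 2 doses were lowered partly because of tolerability findings, so the dose after a recurrent toxicity should be unambiguous here.

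Three nearby dosing or medication instructions also need correcting:

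- the Schedule 1 restart after Grade 3 or worse thrombocytopenia with bleeding;
- the Schedule 2 first-occurrence diarrhea restart;
- the guidance on S-adenosylmethionine (SAM) and N-acetylcysteine (NAC).

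**Working it through.** No sample size, power or error rate is involved, and the plan gives no figure to reproduce. The check sets Table 4 against Tables 2 and 3 and the escalation doses in Section 6.3.1. Weekly dose = mg/m² per dose × doses per week.

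**Second occurrence: is the next level down twice weekly?** The ladders do not list the escalated dose, so level 0 is taken as one level below it.

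| Position | Current, mg/m²/week | Next level down, mg/m²/week | Twice weekly? |
|---|---|---|---|
| Part 1 escalated | 60 × 2 = 120 | 50 × 2 = 100 | Yes |
| Part 1 level 0 | 50 × 2 = 100 | 35 × 2 = 70 | Yes |
| Part 1 level -1 | 35 × 2 = 70 | 50 × 1 = 50 | No |
| Part 1 level -2 | 50 × 1 = 50 | 35 × 1 = 35 | No |
| Part 1 level -3 | 35 × 1 = 35 | Discontinue | n/a |
| Schedule 1 escalated | 50 × 2 = 100 | 35 × 2 = 70 | Yes |
| Schedule 1 level 0 | 35 × 2 = 70 | 50 × 1 = 50 | No |
| Schedule 1 level -1 | 50 × 1 = 50 | 35 × 1 = 35 | No |
| Schedule 1 level -2 | 35 × 1 = 35 | Discontinue | n/a |

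The restart instruction conflicts with the ladder in the four rows marked No.

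**Possible readings at Schedule 1 level 0 (70 mg/m²/week):**

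- Level -1 as Table 3 defines it: 50 × 1 = 50, and 50/70 = 0.71 (-29%). This drops the words twice weekly.
- The level -1 amount given twice weekly: 50 × 2 = 100, and 100/70 = 1.43 (+43%). This equals the escalated dose in Section 6.3.1, which requires no major toxicity and sponsor approval.
- 35 mg/m² twice weekly: 35 × 2 = 70. This is no reduction.

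Only the first is a reduced level in Table 3. Section 6.3 and the closing notes to Table 4 both send modifications to Tables 2 and 3, which makes it the most likely intention.

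**Dose while diarrhea is active, Schedule 1 level 0.** First episode: 35 × 1 = 35 mg/m²/week. Second episode as written, one level down and once weekly: 50 × 1 = 50. Since 50/35 = 1.43, the recurrent episode would be managed at a 43% higher weekly dose than the first. The same arithmetic (35 against 50) applies at Part 1 level -1 if both episodes occur there.

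**First-occurrence clause.** It presupposes a patient on twice-weekly dosing. Someone already at a once-weekly level is not provided for. Table 4 itself creates that state, since Grade 3 or worse thrombocytopenia without bleeding leads to 50 mg/m² once weekly in both columns.

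**Related cells:**

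- *Thrombocytopenia with bleeding, Schedule 1.* The cell gives 35 mg/m² once weekly and also level -1, which is 50 mg/m² once weekly. In Schedule 2 the two coincide, because level -1 there is 35 mg/m² once weekly. Part 1 gives only 35 mg/m² once weekly.
- *Schedule 2 diarrhea, first occurrence.* Applied literally to a patient already at level -1, restarting at level 0 moves her from 35 to 50 mg/m² once weekly.
- *SAM and NAC.* Table 4 (AST/ALT Grades 2 and 3) suggests SAM, and Section 6.5.3 allows either agent for suspected selinexor liver dysfunction. Section 6.4.2.4 tells patients not to take them and states no exception.

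**The case against.** The strongest reply is that the ladders already give the answer. Each level is an amount with a frequency, and the only level directly below Schedule 1 level 0 is 50 mg/m² once weekly. The synopsis, Section 3.1.1 and SAP Section 1.2.1.1 also allow dose changes in consultation with a sponsor representative, so a site in doubt has someone to ask. The wording works at the Part 1 starting dose, and Part 1 planned about 3 × 21 = 63 patients against about 16 on Schedule 1. The trigger is narrow: a second episode despite maximal anti-diarrheal medication. For SAM and NAC, Section 6.4.2.4 can be read as a general bar on patient use, with Table 4 and Section 6.5.3 as the clinician-directed exception.

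Much of this stands, and it limits the consequences. It does not remove the conflict. The ladder gives a usable dose only if the words twice weekly are disregarded, and nothing in the protocol tells the site to do that. Section 6.3 refers re-escalation to the text for the specific toxicity, which for diarrhea is this same cell. The separate re-escalation paragraph after Table 4 names neutropenia, anorexia and fatigue, not diarrhea. Consultation does not correct the two restart doses in the Schedule 1 bleeding cell either.

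Two stronger readings are tempting. A reader might infer that the protocol directs a dose increase to 100 mg/m²/week. The documents do not support that: it takes the amount from a level and discards its frequency, turns an instruction to reduce into an increase, and bypasses the conditions in Section 6.3.1. A reader might also infer that the first-occurrence clauses contradict the ladders. They are better described as silent on patients who have already been reduced.

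**Conclusion.** The second-occurrence restart is wrong as written for Schedule 1 levels 0 and -1 and for Part 1 levels -1 and -2. The conflict lies between Table 4 and the ladders it depends on. The intended dose from Schedule 1 level 0 is most likely 50 mg/m² once weekly; this is an inference from the references to Tables 2 and 3, because no text states it. Grade 3/4 diarrhea inherits the problem only where the conflicting clause applies.

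It should be corrected because it is a current safety dosing rule, but the practical effect is small. Section 1.4 reports 3 patients on treatment in July 2016 and does not give their schedule. Under Section 18 (Appendix 16) they finish their current cycle and move to the Maintenance Phase, where dose changes are discussed with the Medical Monitor. The documents give no frequency for recurrent diarrhea, so the number of patients affected cannot be estimated. No endpoint or analysis is affected.

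**What to change.** In the Part 1 and Schedule 1 cells for Grade 2 diarrhea:

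- **First occurrence, restart:** *re-start at the current dose level and frequency.* For a patient already on once-weekly dosing, the once-weekly hold then changes nothing; if the sponsor wants a reduction there, the cell should say so.
- **Second occurrence, restart:** *continue at the reduced level's dose and frequency per Table 2 or Table 3; if that level is Discontinue dosing, stop.*
- **Dose during active recurrent diarrhea, Schedule 1 level 0:** state it, for example 35 mg/m² once weekly, so that it does not exceed the first-episode hold of 35 mg/m² once weekly. The same sentence could cover Part 1 level -1.

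Secondary corrections:

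- In the Schedule 1 cell for Grade 3 or worse thrombocytopenia with bleeding, delete the restart at level -1 and keep 35 mg/m² once weekly, the dose in the other two columns.
- In the Schedule 2 diarrhea cell, limit the restart at level 0 to patients who were at level 0 when the episode began.
- In Section 6.4.2.4, add an exception for investigator-directed SAM or NAC, to agree with Table 4 and Section 6.5.3.

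The cost is wording in two Table 4 rows and one sentence in Section 6.4.2.4, with no extra patients, visits or procedures. Section 11 requires modifications by amendment, with prior approval unless the change removes an immediate hazard or is non-substantial and only logistical or administrative. A dosing-rule edit may therefore need that process, for a change that few remaining patients could benefit from.

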6.3.3 Selinexor Dose Reduction in the Setting of Infection

Patients with active uncontrolled infections should have selinexor treatment withheld until the infection has resolved or the patient is clinically stable. After the infection has stabilized clinically or resolved, selinexor treatment may continue at the original dose. Missed doses will not be replaced. Patients may continue on antibiotics for prolonged periods while re-initiating their selinexor regimen at the discretion of the Investigator. Prophylactic antibiotics are permitted concurrently with selinexor treatment, but are not required. Opportunistic infections related to selinexor therapy have not been reported in 730 patients evaluable for safety as of 31 May 2015.

6.3.4 Dose Adjustments with Changes in BSA

Dose adjustments do not need to be made for weight gains/losses of $\leq 20\%$. For patients dosed on a mg/m^2 basis, patients with a Body Surface Area (BSA) of greater than 2.5 m^2 will receive a doses of selinexor based on a BSA of 2.5 m^2 . For patients receiving selinexor doses of 60 mg or 80 mg, BSA will be calculated to ensure that the 60 mg or 80 mg dose does not result in a dose $> 70 \text{ mg}/\text{m}^2$. If a patient's dose will exceed this limit, the Investigator should contact the Medical Monitor prior to administration to discuss appropriate dosing.

6.3.5 Missed or Vomited Doses

For once weekly dosing, a maximum of one dose may be given per week; for twice weekly dosing, a maximum of two doses may be given per week. Doses should not be administered less than 5 days apart for once weekly dosing and less than 36 hours apart for once weekly dosing. Every effort should be made to avoid missed doses.

Missed doses

Doses held due to AE(s) will not be considered missed.

Vomited doses

If a dose is vomited within one hour of ingestion, it will be replaced. If vomiting occurs more than 1 hour after dosing, it will still be considered a complete dose.

6.3.6 Dose Adjustments with impressive tumor response

If the shrinkage of the tumor is $\geq 50\%$ compared to the baseline tumor assessment, the dose of selinexor may be reduced to once-weekly dosing.

6.4 Concomitant Medication and Treatment

Concomitant medication is defined as any prescription or over-the-counter preparation, including vitamins and supplements. Patients may continue their baseline medication(s). All concomitant medication(s) must be reported in the case report form (CRF). Any diagnostic, therapeutic or surgical procedure performed during the study period should be recorded, including the dates, description of the procedure(s) and any clinical findings.

6.4.1 Permitted Concomitant Medication

Patients will receive concomitant medications to treat symptoms, adverse events and intercurrent illnesses that are medically necessary as standard care. Medications to treat concomitant diseases like diabetes, hypertension, etc. are allowed.

6.4.1.1 Prevention of Pregnancy

Patients should not become pregnant or father a child while on this study because the drugs in this study can affect an unborn baby. Women should not breastfeed a baby while on this study. It is important that patients understand the need to use birth control while on this study. A woman of childbearing potential is defined as a premenopausal female capable of becoming pregnant. This includes women on oral, injectable or mechanical contraception; women who are single and women whose male sexual partners have been vasectomized or whose male sexual partners have received or are utilizing mechanical contraceptive devices. Female patients of childbearing potential must have a negative serum pregnancy test at screening and agree to use reliable methods of contraception for three months after their last dose of medication. Such methods include intrauterine devices, hormonal contraceptives [contraceptive pills, implants, transdermal patches, hormonal vaginal devices or injections with prolonged release], abstinence or sterilization of the partner. Male patients must use a reliable method of contraception (abstinence or contraception with one of the above-described methods for your partner) if sexually active with a female of childbearing potential. Total (true) abstinence (when this is in line with the preferred and usual lifestyle of the patient), is an acceptable method of contraception. Periodic abstinence (e.g., calendar, ovulation, symptothermal, post-ovulation methods) and withdrawal are not acceptable methods of contraception. For both male and female patients, effective methods of contraception must be used throughout the study and for three months following the last dose.

6.4.1.2 Use of Blood Products

During the administration of selinexor, patients may receive red blood cell (RBC) or platelet transfusions, if clinically indicated, per institutional guidelines. Patients who require repeated transfusion support should be discussed with the Investigator, Sponsor and Medical Monitor.

Appropriate anti-coagulation is allowed during the study (e.g., LMW heparin, direct factor Xa inhibitors). Warfarin is allowed during the study provided that patients are monitored for INR twice a week during the first two cycles of therapy, then weekly to biweekly thereafter.

Patients may receive supportive care with erythropoietin, darbepoetin, G-CSF or GM-CSF, pegylated growth factors, and platelet stimulatory factors, in accordance with clinical practice or institutional guidelines prior to entry and throughout the study.

6.4.1.3 Glucocorticoid therapy

Ongoing glucocorticoids (e.g., \leq 10 mg oral prednisone [or equivalent]) per day are permitted at baseline and during the study for non-malignant conditions (i.e., asthma) as needed.

As part of supportive care (e.g., for nausea or anorexia), oral dexamethasone, up to 40 mg/week, may be given to patients, in consultation with the Medical Monitor. Dexamethasone (4-12 mg) or prednisone (10-20 mg) on days of (\pm 1 day after) selinexor dosing (\pm 1 day after) may improve appetite, reduce nausea or vomiting, and minimize fatigue.

6.4.2 Restricted and Prohibited Medications

6.4.2.1 Concurrent Therapies

Concurrent therapy with any other approved or investigative anticancer therapeutic is not allowed. Other investigational agents should not be used during the study. Use of any immunosuppressive agents during the study must be confirmed by the Medical Monitor. Note that the use of denosumab is not allowed.

6.4.2.2 Alcohol (ethanol)

Ethanol should be avoided on selinexor dosing days as it may compete for glutathione (GSH)-mediated metabolism.

6.4.2.3 Acetaminophen (paracetamol) containing medications

There are no longer any restrictions on the use of acetaminophen (paracetamol) or acetaminophen (paracetamol) -containing products in combination with selinexor, EXCEPT on days of selinexor dosing, when acetaminophen (paracetamol) must not exceed a total daily dose of 1 gram. Although acetaminophen (paracetamol) use in combination with selinexor was restricted in previous selinexor studies based on theoretical interactions with GSH, ongoing clinical safety evaluations on the use of these drugs together have not shown any significant clinical or laboratory abnormalities with doses of acetaminophen (paracetamol) of up to 1 gram and selinexor up to 55 mg/m² (approximately 80-100 mg).

6.4.2.4 Miscellaneous

Patients should not take glutathione (GSH)-, S-adenosylmethionine (SAM)-, or N-acetylcysteine (NAC)-containing products during their participation in this study, as these products may enhance the metabolism of selinexor. See [Appendix 15](#) for a list of representative products. Patients must report all prescription and non-prescription medicines to their physicians during this study.

6.5 Supportive Care Guidelines

6.5.1 Required Supportive Care Medication

5-HT3 Antagonists

In order to minimize nausea, unless contraindicated, all patients must receive 5-HT3 antagonists (ondansetron 8 mg or equivalent) starting before the first dose of selinexor and continued 2-3 times a day, as needed. Alternative anti-emetic therapy may be used for patients who cannot tolerate 5-HT3 antagonists.

6.5.2 Supportive Care Recommendations for Selinexor-Related Adverse Events

Supportive measures for optimal medical care should be provided during participation in this clinical trial. Based on clinical observations in over 560 adult patients treated with selinexor with evaluable safety data as of 01 February 2015, the main side effects are primarily related to anorexia with poor caloric and fluid intake, fatigue, and nausea. Thrombocytopenia also occurs, although it is rarely associated with bleeding.

Besides the required 5-HT3 (Section 6.5.1), supportive care including anti-nausea / anti-emetic therapy, acid suppression (proton pump inhibitors and/or H2-blockers) and other treatments may be administered as described below:

1. Glucocorticoids: dexamethasone (4-12 mg) or equivalent glucocorticoid (e.g., prednisone 10-20 mg) on days of, and 1 day after, selinexor dosing may improve appetite, reduce nausea or vomiting, and minimize fatigue. A maximum of 40 mg dexamethasone or equivalent may be given per week.
2. Appetite stimulants: megestrol acetate at a dose of 80-400 mg daily.
3. Centrally acting agents: per National Comprehensive Cancer Network® (NCCN) Clinical Practice Guidelines® for antiemesis⁹⁸ and anorexia/cachexia (palliative care)⁹⁹ see [Appendix 10](#) (antiemesis) and [Appendix 11](#) (anorexia), respectively.
4. NK1R antagonist: aprepitant or equivalent should be considered and will be covered for selected patients who have severe nausea and vomiting.

